6.6.2 Permitted Concomitant Medications

Investigators may prescribe concomitant medications or treatments (e.g., acetaminophen, diphenhydramine) deemed necessary to provide adequate prophylactic or supportive care except for those medications identified as “excluded” as listed in Section 6.6.3 below.

6.6.3 Excluded Concomitant Medications

The following medications are considered exclusionary during the study:

1. Any investigational anticancer therapy other than the protocol specified therapies
2. Any concurrent chemotherapy, radiotherapy (except palliative radiotherapy), immunotherapy, biologic or hormonal therapy for cancer treatment. Concurrent use of hormones for noncancer-related conditions (e.g., insulin for diabetes and hormone replacement therapy) is acceptable. NOTE: Local treatment of isolated lesions for palliative intent is acceptable (e.g., by local surgery or radiotherapy).
3. Immunosuppressive medications including, but not limited to systemic corticosteroids at doses not exceeding 10 mg/day of prednisone or equivalent, methotrexate, azathioprine, and TNF- α blockers. Use of immunosuppressive medications for the management of investigational product-related AEs or in subjects with contrast allergies is acceptable. In addition, use of inhaled and intranasal corticosteroids is permitted. A temporary period of steroids will be allowed for different indications, at the discretion of the principal investigator (e.g., chronic obstructive pulmonary disease, radiation, nausea, etc.).
4. Live attenuated vaccines within 30 days of durvalumab and tremelimumab dosing (i.e., 30 days prior to the first dose, during treatment with durvalumab and tremelimumab for 30 days post discontinuation of durvalumab and tremelimumab. Inactivated vaccines, such as the injectable influenza vaccine, are permitted.
5. Use of strong CYP3A inhibitors **must** be avoided: The use of any natural/herbal products or other “folk remedies” should be discouraged but use of these products, as well as use of all vitamins, nutritional supplements and all other concomitant medications must be recorded in the eCRF.
 - Olaparib is an FDA approved drug for the treatment of patients with deleterious germline BRCA mutated advanced ovarian cancer. Based on in vitro data and clinical exposure data, olaparib is considered unlikely to cause clinically significant drug interactions through inhibition or induction of cytochrome P450 enzyme activity. In vitro data have, however, also shown that the principal enzyme responsible for the formation of the 3 main metabolites of olaparib is CYP3A4 and consequently, to ensure patient safety, the following potent inhibitors of CYP3A4 must not be used during this study for any patient receiving olaparib.
 - While this is not an exhaustive list, it covers the known potent inhibitors, which have most often previously been reported to be associated with clinically significant drug interactions: ketoconazole, itraconazole, ritonavir, idinavir, saquinavir, telithromycin, clarithromycin and nelfinavir. For patients taking any of the above, the required wash-out period prior to starting olaparib is one week.
6. Use of strong CYP3A inducers **must** be avoided: In addition, to avoid potential reductions in exposure due to drug interactions and therefore a potential reduction in efficacy, the following CYP3A4 inducers **must** be avoided: Phenytoin, rifampicin, rifapentine, rifabutin, carbamazepine, phenobarbitone, nevirapine, modafinil and St John’s Wort (*Hypericum perforatum*). For patients taking any of the above, the required wash-out periods prior to starting olaparib are: phenobarbitone 5 weeks, and for any of the others, 3

weeks. After randomization, if the use of any potent inducers or inhibitors of CYP3A4 are considered necessary for the patient's safety and welfare, the Investigator must contact the AstraZeneca Study Physician. A decision to allow the patient to continue in the study will be made on a case-by-case basis.

7. Olaparib in combination with other myelosuppressive anticancer agents, including DNA damaging agents, indicate a potentiation and prolongation of myelosuppressive toxicity.

Table 3 Prohibited Medications

Prohibited Medication/ Class of Drug	Usage
Additional investigational anticancer therapy concurrent with those under investigation in this study	Should not be given while the patient is on IP treatment
mAbs against CTLA-4, PD-1, or PD-L1	Should not be given whilst the patient is on IP treatment through 90 days after the last dose of IP.
Any concurrent chemotherapy, local therapy (except palliative radiotherapy for non-target lesions, e.g., radiotherapy, surgery, radiofrequency ablation), biologic therapy, or hormonal therapy for cancer treatment	Should not be given whilst the patient is on IP treatment (including SOC). Concurrent use of hormones for non-cancer related conditions (e.g., insulin for diabetes and hormone replacement therapy) is acceptable.
Immunosuppressive medications, including, but not limited to, systemic corticosteroids at doses exceeding 10 mg/day of prednisone or its equivalent, methotrexate, azathioprine, and tumor necrosis factor α blockers	Should not be given whilst the patient is on IP treatment (including SOC). Use of immunosuppressive medications for the management of IP related AEs or in patients with contrast allergies is acceptable. In addition, use of inhaled, topical, and intranasal corticosteroids is permitted.
Live attenuated vaccines	Should not be given through 30 days after the last dose of IP (including SOC) during the study

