If new or worsening pulmonary symptoms (e.g. dyspnea) or radiological abnormality occurs, an interruption in olaparib dosing is recommended and a diagnostic workup (including a high-resolution CT scan) should be performed, to exclude pneumonitis. Following investigation, if no evidence of abnormality is observed on CT imaging and symptoms resolve, then olaparib treatment can be restarted, if deemed appropriate by the investigator. If significant pulmonary abnormalities are identified, these need to be discussed with the AstraZeneca Study Physician.

All dose reductions and interruptions (including any missed doses), and the reasons for the reductions/interruptions are to be recorded in the eCRF.

Olaparib should be stopped before surgery and re-started after wound has healed following recovery.

No stoppage of olaparib is required for any biopsy procedures.

Olaparib should be discontinued for a minimum of 7 days before a patient undergoes therapeutic palliative radiation treatment.

Management of nausea and vomiting

Events of nausea and vomiting are known to be associated with olaparib treatment. In study D0810C00019 nausea was reported in 71% of the olaparib treated patients and 36% in the placebo treated patients and vomiting was reported in 34% of the olaparib treated patients and 14% in the placebo treated patients. They are generally mild to moderate (CTCAE grade 1 or 2) severity, intermittent and manageable on continued treatment. The first onset generally occurs in the first month of treatment with the incidence of nausea and vomiting not showing an increase over the treatment cycles.

No routine prophylactic anti-emetic treatment is required at the start of study treatment, however, patients should receive appropriate anti-emetic treatment at the first onset of nausea or vomiting and as required thereafter, in accordance with local treatment practice guidelines.

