6.6.4 Supportive Care

Table 4 Rescue Medications

Rescue and Supportive Care Medication/ Class of Drug	Usage
Concomitant medications or treatments (e.g., acetaminophen or diphenhydramine) deemed necessary by the Investigator to provide adequate prophylactic or supportive care, except for those medications identified as “excluded” as listed above.	To be administered as prescribed by the Investigator
Best supportive care (including antibiotics, nutritional support, growth factor support, correction of metabolic disorders, optimal symptom control, and pain management [including palliative radiotherapy, etc.]).	Should be used when necessary for all patients

Participants may be pretreated for nausea and vomiting with appropriate anti-emetics.

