17. CT (preferred) or MRI scans, preferably with IV contrast, are collected during screening (for baseline), as close to and prior to initiation of study treatment. Timing of on-treatment CT/MRI scans is pre-dose C4D1 (± 7 days) for biopsy site determination and every 3 cycles thereafter (i.e. Day 1 of Cycles 7, 10, 13 ± 7 days) or as clinically indicated until progressive disease or off-study. Response according to irRECIST criteria (irCR, irPR) requires a confirmatory scan preferably at the next regularly scheduled imaging visit and no earlier than 6 weeks after the prior assessment of CR, PR, or SD is deemed by irRECIST. End of Treatment disease assessment does not need to be repeated if performed within 28 days prior to end of treatment.
18. Refer to Table 7 for details.
19. Refer to Appendix H and Appendix I for follow-up visits.
20. Results from CA-125 and thyroid function test do not need to be available prior to dosing patient on dosing days.

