8.5.1.2 Fresh tumor biopsies

Tumor lesions planned for biopsy must not be used as index lesions for assessment of disease and tumor response. Excisional biopsies are preferred where clinically appropriate. Otherwise, subjects will undergo 4 image-guided core biopsies (18 g or larger, if clinically appropriate). Two tissue cores will be placed in formalin and processed to FFPE. The remaining 2 cores will be immediately frozen in liquid nitrogen and then stored at -80°C. Network sites will ship the samples in formalin at room temperature on the same day as collection to the central lab (IAF) as per lab manual. Flash frozen samples can be batch shipped to the Central Lab on dry ice.

Additional details for sample collection, processing, storage, and shipment is provided in the ***Laboratory Manual [RPCI Immune Analysis Facility study Laboratory Manual (Version 2.0)]***.

Tumor biopsy will be performed on Cycle 4 Day 1 ± 7 days (if clinically appropriate), or at time of progression (if clinically appropriate). Archived sample will be utilized for baseline assessment.

Note: All investigator or analyzing research laboratories housing research samples need to maintain current **Temperature Logs** and study-specific **Sample Tracking and Shipping Logs**. The Principal Investigator/Laboratory Manager **must** ensure that the stated lab(s) have a process in place to document the receipt/processing/storage/shipping of study-related samples/specimens. This is required for both observational and interventional clinical studies collecting clinical samples.

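### Section 6.6.3 permits palliative local treatment of a measured lesion in one place and bars it in another; a site following the permissive text could hide progression in the primary count R

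*Combined protocol and SAP*

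**What the plan says.** Four places govern local treatment during the study.

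- **Section 6.6.3, item 2** lists as exclusionary "Any concurrent chemotherapy, radiotherapy (except palliative radiotherapy), immunotherapy, biologic or hormonal therapy for cancer treatment". Palliative radiotherapy is thus exempt, whichever lesion is treated. The NOTE goes further: "Local treatment of isolated lesions for palliative intent is acceptable (e.g., by local surgery or radiotherapy". It names surgery and does not mention target lesions.
- **Section 6.6.3, Table 3** prohibits on treatment "local therapy (except palliative radiotherapy for non-target lesions, e.g., radiotherapy, surgery, radiofrequency ablation". The exception is limited to non-target lesions. The position of the examples leaves it unclear whether surgery and ablation illustrate the ban or the exception.
- **Section 6.6.4, Table 4** lists supportive care that includes "optimal symptom control, and pain management [including palliative radiotherapy, etc", without reference to lesion type.
- **Section 8.5.1.2**, on biopsies, states: "Tumor lesions planned for biopsy must not be used as index lesions for assessment of disease and tumor response". The intention to keep measured lesions undisturbed is therefore visible elsewhere in the protocol.

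On assessment, Appendix K 2.1 adds target and new measured lesions into the total measured tumor burden (TMTB). Appendix K 2.4 defines irPD as a rise in TMTB of at least 20% and at least 5 mm over nadir, or progression in non-target or new non-measurable lesions. Section 12.4 tests R, the number of non-progressors in both strata, at 3 months (resistant) and 6 months (sensitive). Table 5, footnote 17 sets the imaging: "Timing of on-treatment CT/MRI scans is pre-dose C4D1", then every three cycles, "or as clinically indicated until progressive disease or off-study".

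**The concern.** A site asked to irradiate or remove a painful target lesion is told yes by the NOTE and no by Table 3. If it follows the NOTE, a growing lesion leaves the sum or shrinks for a reason unrelated to study drug. Where progression would have shown only in TMTB, the patient is then counted as progression-free. The error always favours the treatment.

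The resistant stratum matters most. It supplies 18 of the 27 patients, and the only scheduled on-treatment scan by its 3-month landmark is Cycle 4 Day 1 (week 12). The sensitive stratum has a second scheduled scan at Cycle 7 Day 1 (week 24) before its landmark. Treating a lesion also lowers the nadir, which makes later irPD easier to reach, but for resistant patients the next scheduled scan falls after their landmark.

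**Working it through.** **Inputs (Section 12.4).** Stratum sizes 18 and 9; null rates 0.55 and 0.65; alternatives 0.55 + 0.20 = 0.75 and 0.65 + 0.15 = 0.80; alpha 0.10, with the alternative above the null; stated power 0.72.

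**The plan's own figure.** Take R = Bin(18, p1) + Bin(9, p2), by exact convolution with fixed strata.

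- Under the null, P(R ≥ 19) = 0.140 and P(R ≥ 20) = 0.068, so the cut-off is R ≥ 20.
- Under the alternative, P(R ≥ 20) = 0.717, which reproduces the stated 0.72.

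**Lesion illustration (sizes invented).** Two targets of 40 and 30 mm give a baseline sum of 70 mm. The first grows to 55 mm: 55 + 30 = 85 mm, a rise of 15 mm and 15/70 = 21.4%, which is irPD. If that lesion is resected before the scan, the sum is 30 mm, a change of (30 − 70)/70 = −57.1%, and irPD by TMTB is not met. From the 30 mm nadir a later rise of 6 mm (20%) is irPD; from 70 mm it would have taken 14 mm.

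**Effect on the test.** Let q be the share of true progressors hidden this way. The documents give no value, so q is assumed and shown as a range. With null rates p1 = 0.55 + 0.45q and p2 = 0.65 + 0.35q (or one stratum left unchanged), the exact P(R ≥ 20) is:

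| q | Resistant only | Both strata | Sensitive only |
|---|---|---|---|
| 0 | 0.068 | 0.068 | 0.068 |
| 2% | 0.077 | 0.080 | 0.071 |
| 5% | 0.092 | 0.102 | 0.076 |
| 10% | 0.121 | 0.147 | 0.085 |

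The resistant-only column fits the mechanism best. It passes 0.10 at q = 6.5%, which is 0.065 × (18 × 0.45 = 8.1 expected progressors) = 0.53 patients on average. With both strata affected, an upper bound, the crossing is at q = 4.8%, or 0.53 of 8.1 + 9 × 0.35 = 11.25 expected progressors.

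**Cost of scoring treated patients as failures.** Let f be the share of truly progression-free patients who have a measured lesion treated (also assumed). Using alternative rates 0.75(1 − f) and 0.80(1 − f), or reducing only the resistant rate, power at R ≥ 20 falls from 0.717 to:

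| f | Both strata | Resistant only |
|---|---|---|
| 1% | 0.684 | 0.696 |
| 2% | 0.649 | 0.673 |
| 5% | 0.54 | 0.60 |
| 10% | 0.37 | 0.49 |

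**The case against.** **The restriction is already there.** Section 6.6.1 ends by sending the reader to the tables, and Table 3 carries the non-target limit, so the specific table could be read as narrowing the general NOTE. That is a sensible reading, but the protocol states no order of precedence, and the NOTE names surgery as acceptable. The conflict stands.

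**Other routes to progression remain.** Unscheduled scans are allowed, and non-target or new non-measurable lesions can still give irPD. Section 9 waives confirmation of PD for rapid progression needing other anti-cancer therapy and for symptomatic progression needing urgent intervention. All of this stands. What is left is mainly less urgent palliation of a measured lesion, with no scan beforehand and no progression elsewhere.

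**RECIST 1.1 may govern.** Section 9 says efficacy endpoints will be derived by RECIST 1.1, in which case TMTB would not be the operative measure. Section 9.1 and Appendix K 2.4, however, say RECIST 1.1 will not determine progression, and Appendix K 2.4 assigns the formal analysis to irRECIST. The TMTB argument rests on those two places; the conflict between the NOTE and Table 3 does not.

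**Readings that go too far.** A reader might infer that the criteria have no rule for a lesion treated on study. Appendix K 1.8 deals only with lesions treated before target selection, and irNE is generic, but Appendix K is a summary of cited papers that were not available, so its silence does not show that the full criteria are silent. A reader might also infer that treated patients must be failures in the primary analysis. That is one convention among several, it misclassifies patients who are truly progression-free, and the power losses above argue against imposing it.

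**Conclusion.** The inconsistency is real and should be corrected. Item 2 and its NOTE permit what Table 3 prohibits, and following them can bias R in favour of treatment, chiefly in the resistant stratum.

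The size of that bias is unknown. It would be tempting to conclude that the trial's type I error exceeds 0.10, but the documents do not support this. The design has exact size 0.068, leaving some room, and crosses 0.10 only above an assumed q of about 6.5% in the resistant stratum. For smaller q in that stratum the test stays within its nominal level, and with only the sensitive stratum affected the size is 0.085 even at q = 10%.

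The conclusion assumes that irRECIST governs progression in R, that some sites act on the NOTE, and that the hidden progression would have been visible only in measured lesions. This is a consistency and endpoint-protection point; the sample-size calculation is not at fault.

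**What to change.** 1. Align item 2 and its NOTE with Table 3: on-treatment palliative local therapy is limited to lesions that are neither target nor new measured lesions. State in both places whether surgery is allowed, and cross-refer Table 4 to the rule.
2. If clinical need requires treating a measured lesion, obtain the clinically indicated scan already permitted by footnote 17 beforehand where feasible, and record which lesion was treated and when.
3. In Section 12.4, add a sensitivity analysis of R that counts such patients as not progression-free. The primary analysis need not do so.

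The cost is wording edits, slightly narrower options for local palliation while on study drug, and one new data item. Existing records do not supply that item: Section 6.5 requires "All dose reductions and interruptions (including any missed doses), and the reasons for the reductions/interruptions are to be recorded in the eCRF", which may show that olaparib was stopped for surgery or radiation, but does not ask which lesion was treated or whether it was a target. Palliation that is clinically necessary is not withheld, and the power of the primary test is unchanged by the sensitivity analysis.

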5.2 Exclusion Criteria

Participants will be excluded from this study for the following:

1. Involvement in the planning and/or conduct of the study (applies to both AstraZeneca staff and/or staff at the study site). Previous enrollment in the present study.
2. Participation in another clinical study with an investigational product during the last 4 weeks (prior use of bevacizumab in the upfront setting is allowed).
3. History of discontinuation of any previous treatment with PARP inhibitors, including olaparib, or a PD-1 or PD-L1 inhibitor, including durvalumab or anti-CTLA4 antibody, including tremelimumab due to toxicity.
4. Patients with myelodysplastic syndrome/acute myeloid leukemia.
5. History and/or confirmed ILD/pneumonitis, extensive bilateral lung disease on HRCT scan.
6. Concomitant use of a strong CYP3A inhibitors (e.g., itraconazole, telithromycin, clarithromycin, ketoconazole, voriconazole, nefazodone, posaconazole, ritonavir, lopinavir/ritonavir, indinavir, saquinavir, nelfinavir, boceprevir, telaprevir) and moderate CYP3A inhibitors (e.g., amprenavir, aprepitant, atazanavir, ciprofloxacin, crizotinib, darunavir/ritonavir, diltiazem, erythromycin, fluconazole. Fosamprenavir, imatinib, verapamil).
7. Concomitant use of strong CYP3A inducers (e.g., phenytoin, rifampicin, carbamazepine, St. John's Wort) and moderate CYP3A inducers (e.g., bosentan, efavirenz, etravirine, modafinil, nafcillin).
8. History of another primary malignancy except for:
 - Malignancy treated with curative intent and with no known active disease ≥ 5 years before the first dose of study drug and of low potential risk for recurrence.
 - Adequately treated non-melanoma skin cancer or lentigo maligna without evidence of disease (e.g. basal cell or squamous cell carcinoma of the skin).
 - Adequately treated carcinoma in situ without evidence of disease (e.g., breast and cervical cancer in situ).
9. Receipt of the last dose of anti-cancer therapy (chemotherapy, immunotherapy, endocrine therapy, targeted therapy, biologic therapy, tumor embolization, monoclonal antibodies,

radiotherapy or other investigational agent) \leq 21 days prior to the first dose of study drug and within 6 weeks for nitrosourea or mitomycin C).

10. Mean QT interval corrected for heart rate (QTcF) \geq 470 ms calculated from 3 electrocardiograms (ECGs) using Fridericia's Correction.
11. Patients with history of myocardial infarction within 6 months.

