6.2.1.2 Duration of Treatment and Criteria for Retreatment

For patients receiving durvalumab + tremelimumab + olaparib, retreatment is allowed (once only) for patients meeting the retreatment criteria below. The same treatment guidelines followed during the initial 12-month treatment period will be followed during the retreatment period, including the same dose and frequency of treatments and the same schedule of assessments. Similar to the initial treatment, in the event of disease progression while the patient is receiving durvalumab and olaparib alone (i.e. after completion of the first 4 doses of tremelimumab), the patient may be given an additional 4 doses of tremelimumab per the investigator's discretion, in combination with the ongoing durvalumab and olaparib.

Patients receiving the combination of durvalumab, tremelimumab, and olaparib may undergo retreatment in the clinical scenarios described below:

- Patients who achieve and maintain disease control (i.e., irCR, irPR, or irSD) through to the end of the 12-month treatment period may restart treatment with the combination upon evidence of PD according to irRECIST during follow-up.

- Before restarting their assigned treatment, the Investigator should ensure that the patient:
 - Does not have any significant, unacceptable, or irreversible toxicities that indicate continuing treatment will not further benefit the patient.
 - Still fulfills the eligibility criteria for this study, including re-consenting to restart durvalumab, tremelimumab, and olaparib.
 - Has not received an intervening systemic anticancer therapy after their assigned treatment discontinuation.
 - Has had a baseline tumor assessment within 28 days of restarting their assigned treatment; all further scans should occur with the same frequency as during the initial 12 months of treatment (relative to the date of randomization) until study treatment is stopped (maximum of 12 months of further treatment).

During the retreatment period, patients receiving durvalumab + tremelimumab + olaparib may resume durvalumab dosing at 1500 mg Q4W with 75 mg of tremelimumab Q4W for 4 doses each. Patients will then continue with durvalumab monotherapy at 1500 mg Q4W, beginning at Week 16, 4 weeks after the last dose of combination therapy (a total of 9 additional doses). Olaparib will be administered throughout this retreatment period at 300 mg BID (or the MTD in case of dose de-escalation) for up to 1 year.

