Study treatment can be restarted at the same dose if an adverse event of neutropenia or leukopenia have been recovered up to CTC AE grade >1 (ANC $> 1.5 \times 10^9/L$). Growth factor support should be stopped at least 24h before restarting study drug (7 days for pegylated G-CSF).

Any subsequent interruptions will require study treatment dose reductions.

Management of thrombocytopenia

An adverse event of thrombocytopenia should be managed as deemed appropriate by the investigator. If a patient develops thrombocytopenia CTCAE grade 3 or worse study treatment should be interrupted for a maximum of 4 weeks. In some cases, management of thrombocytopenia may require platelet transfusions. Platelet transfusions should be done according to local hospital guidelines.

Management of prolonged hematological toxicities while on study treatment

If a patient develops prolonged hematological toxicity such as:

- ≥ 2 week interruption/delay in study treatment due to CTC grade 3 or worse anemia and/or development of blood transfusion dependence
- ≥ 2 week interruption/delay in study treatment due to CTC grade 3 or worse neutropenia (ANC $< 1 \times 10^9/L$)
- ≥ 2 week interruption/delay in study treatment due to CTC grade 3 or worse thrombocytopenia (Platelets $< 50 \times 10^9/L$)

Weekly differential blood counts including reticulocytes (calculate reticulocyte index (RI), RI = reticulocyte count x hematocrit (Hct)/normal Hct; a value of 45 is usually used for normal Hct) and peripheral blood smear should be performed. If any blood parameters remain clinically abnormal after 4 weeks of dose interruption, the patient should be referred to hematologist for further investigations. Bone marrow analysis and/or blood cytogenetic analysis should be considered at this stage according to standard hematological practice.

Myelodysplastic syndrome and/or Acute Myeloid Leukemia (MDS/AML is an important potential risk for olaparib. Development of a confirmed MDS or other clonal blood disorder should be

reported as an SAE and full reports must be provided by the investigator to AstraZeneca Patient Safety. Study treatment should be discontinued if diagnosis of MDS/AML is confirmed.

The dose of olaparib **must not** be adjusted under any other circumstances unless the AstraZeneca Study Physician gives prior agreement.

Management of new or worsening pulmonary symptoms

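### Moderate CYP3A inhibitors and inducers are barred at entry but, modafinil apart, are missing from the on-study exclusion list, and the study-physician contact rule covers potent agents only

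*Combined protocol and SAP*

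**What the plan says.** **At entry.** Besides strong agents, exclusion 6 bars "moderate CYP3A inhibitors (e.g., amprenavir, aprepitant, atazanavir, ciprofloxacin, crizotinib" and seven more named drugs. Exclusion 7 bars "moderate CYP3A inducers (e.g., bosentan, efavirenz, etravirine, modafinil, nafcillin" alongside strong inducers. The eligibility verification form signed for each patient repeats both criteria.

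**On study.** Section 6.6.2 lets investigators prescribe what is "deemed necessary to provide adequate prophylactic or supportive care except for those medications identified as" excluded in Section 6.6.3. Table 4 (Section 6.6.4) repeats that default. In Section 6.6.3, item 5 is headed as a rule on strong CYP3A inhibitors, and its operative sentence is that "the following potent inhibitors of CYP3A4 must not be used during this study for any patient receiving olaparib". On the list's scope it adds: "While this is not an exhaustive list, it covers the known potent inhibitors". Item 6 is headed as a rule on strong inducers and names nine agents. The investigator must contact the study physician "if the use of any potent inducers or inhibitors of CYP3A4 are considered necessary". Table 3, the table of prohibited medications, has no CYP3A row.

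**Related rules.** Section 6.5 allows olaparib interruption or reduction for toxicity and otherwise says the dose must not "be adjusted under any other circumstances unless the AstraZeneca Study Physician gives prior agreement". Section 6.2.1.2 allows retreatment only if, among other conditions, the patient "Still fulfills the eligibility criteria for this study, including re-consenting to restart durvalumab, tremelimumab, and olaparib".

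**The concern.** The protocol gives its own reasons for controlling CYP3A. Section 6.6.3 states that CYP3A4 is the main enzyme forming olaparib's three principal metabolites. It restricts inhibitors for patient safety and inducers to avoid losing exposure and efficacy. Section 6.6.1 tells patients to avoid grapefruit and Seville oranges because they may raise olaparib concentrations. An entry bar that includes moderate agents fits that reasoning. An on-study list that stops at strong or potent agents leaves it incomplete over the period when olaparib is actually being taken.

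The drug classes involved are foreseeable. Section 6.5 calls for anti-emetics at the first nausea or vomiting, and Appendix G repeatedly asks sites to consider prophylactic antibiotics and antifungals while steroids are tapered, although study drug may be on hold at that point. Exclusion 6 itself names aprepitant, ciprofloxacin, erythromycin and fluconazole as moderate inhibitors. Two sites could reasonably reach opposite answers on whether a patient on olaparib may take one of these, and a site following Sections 6.6.2 and 6.6.3 as written would not be prompted to ask.

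Retreatment adds an oddity. A moderate agent would block a restart, because eligibility must be met again, yet it is off the list once dosing has resumed.

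**Working it through.** No statistical quantity is involved, so the check is a comparison of the named drugs.

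**Inhibitors**

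- Exclusion 6, moderate (12): amprenavir, aprepitant, atazanavir, ciprofloxacin, crizotinib, darunavir/ritonavir, diltiazem, erythromycin, fluconazole, fosamprenavir, imatinib, verapamil.
- Section 6.6.3 item 5 (8): ketoconazole, itraconazole, ritonavir, indinavir, saquinavir, telithromycin, clarithromycin, nelfinavir. Exclusion 6 classes all eight as strong.
- Overlap with the moderate group: 0 of 12, or 1 of 12 if ritonavir counts for darunavir/ritonavir.

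**Inducers**

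- Exclusion 7, moderate (5): bosentan, efavirenz, etravirine, modafinil, nafcillin.
- Section 6.6.3 item 6 (9): phenytoin, rifampicin, rifapentine, rifabutin, carbamazepine, phenobarbitone, nevirapine, modafinil, St John's Wort.
- Overlap with the moderate group: 1 of 5 (modafinil).
- Of the other eight, four are strong in exclusion 7 (phenytoin, rifampicin, carbamazepine, St John's Wort). Four are not graded there (rifapentine, rifabutin, phenobarbitone, nevirapine) and are strong only by virtue of the item 6 heading.

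**Together:** 12 + 5 = 17 moderate agents are named at entry. Section 6.6.3 items 5 and 6 name 0 + 1 = 1 of them (2 with the ritonavir component), leaving 16 (or 15) unlisted.

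**Does any other text close the gap?**

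1. The statement that the item 5 list is not exhaustive extends it only to further potent inhibitors.
2. The contact rule is also worded for potent agents, so an unlisted moderate agent does not trigger it.
3. Section 6.6.2 points to Section 6.6.3, not to Section 5.2.
4. Section 6.8 item 3 stops treatment for a patient found to have met an exclusion criterion at study entry, where continuing might be a safety risk. It does not address a drug started later.
5. Section 6.6.1 requires the Principal Investigator to be told of all medication and the eCRF to record it. That captures use without restricting it.

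**The case against.** The strongest reply is that no gap exists, because concomitant use in exclusions 6 and 7 already means use alongside study drug. There is textual support. Neither criterion has a look-back window, whereas exclusions 9 and 12 do. Exclusions 24 and 25 plainly reach past entry. Section 6.8 item 3 deals with ineligible enrolments and does not define the scope of exclusions 6 and 7. This is a reasonable reading and it stands as one. It does not settle the matter, because no sentence says so and the on-study sections give a separate, narrower list.

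A second reply is that a looser on-study rule may be deliberate. Inclusion 4 asks for freedom from infection needing antibiotics, while Table 4 allows antibiotics on study. Exclusion 12 limits immunosuppressants before entry, while Section 6.6.3 item 3 allows a temporary course of steroids. That is fair, but in both cases the relaxation is written down. For moderate CYP3A agents it arises only from silence.

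Third, sites are not uninformed. The signed eligibility form names the moderate agents, and Section 1.2.4 expects familiarity with the olaparib Investigator's Brochure, whose interaction advice cannot be seen here. Toxicity can lead to interruption or reduction, and Section 6.5 allows other dose changes with the study physician's agreement. These are real partial safeguards. None states the on-study rule for a moderate agent.

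A reader might go further and infer that patients will be materially over- or under-exposed to olaparib. The documents do not support that. They give no exposure effect for moderate agents, do not grade the grapefruit effect, and base the item 5 list on potent inhibitors most often reported to cause clinically significant interactions. Nor is the Phase II setting one of unreduced olaparib: the dose is 250 mg BID, below the 300 mg BID starting dose.

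**Conclusion.** The point holds as a mismatch between the entry criteria and the operative on-study rule. Of 17 moderate agents named at entry, items 5 and 6 of Section 6.6.3 name one, or two counting ritonavir, and the contact rule covers potent agents only. The consequence, that a moderate agent may be started during olaparib dosing without contacting the study physician, assumes that exclusions 6 and 7 are not read as continuing on treatment. The protocol does not say which reading applies.

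Two stronger conclusions should not be drawn. The protocol does not expressly approve moderate agents on study; the permission follows from the default in Section 6.6.2. The counts also do not measure patient risk: both exclusion lists are examples, other rules may catch some of the agents, and neither the size of any interaction nor its frequency can be established from the documents. The amendment is worth making because it is cheap and follows the protocol's own CYP3A4 rationale. It has no bearing on alpha, power or sample size.

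**What to change.** Amend Section 6.6.3 items 5 and 6 so that the moderate CYP3A inhibitors and inducers of exclusions 6 and 7 are also to be avoided during olaparib treatment. Extend the study-physician contact rule to moderate agents when no alternative is suitable, so that any interruption or dose change is agreed case by case under Section 6.5. If a looser on-study rule is in fact intended, state that exclusions 6 and 7 apply at entry only, and why.

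The cost is a wording amendment and a somewhat narrower choice of anti-emetics, antibiotics and antifungals for sites. The contact rule limits that cost, because it leaves a route for necessary use. Sample size and the primary test are unaffected.
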